In both Lead-in and Efficacy Stages, patients will be screened for study eligibility within 28 days before the first study drug dose after provision of written informed consent. Patients who are determined to be eligible, based on Screening assessments, will be enrolled in the study on Cycle (C)1, Day (D)1 (Baseline, before the first dose of BXCL701).

During treatment, patients will attend study center visits and have study evaluations performed as detailed in the Schedule of Assessments (Appendix A). All study visits will

be conducted on an outpatient basis but may be conducted on an inpatient basis per the investigator's judgement.

All patients must have pre-treatment (prior to study treatment dosing) imaging (computed tomography [CT] scan of chest/abdomen/pelvis or magnetic resonance imaging [MRI] for baseline tumor measurements, as well as bone scintigraphy [BS, if deemed necessary]). Patients with skin, subcutaneous or lymph node metastases may also have tumor evaluations (including measurements, with a ruler) by means of physical examination. Patients with a history of central nervous system (CNS) malignant involvement or CNS symptoms should have either CT or MRI imaging of the brain performed to assess active CNS malignancy.

Tumor measurements and disease response assessments (CT or MRI; BS) are also to be performed at the end of Cycle 3 (approximately 9 weeks after the first study treatment dose), and then approximately every 9 weeks thereafter until development of progressive disease (PD). Intervals can be shortened to 6 weeks if clinically necessary per treating physician. For patients with evidence of disease control (stable disease or better) at Week 27, tumor measurements and disease response assessments may be performed less frequently (approximately every 12 weeks) thereafter. Tumor measurements and disease response assessments also are to be performed at the End of Treatment (EOT) visit.

Study procedures are listed in Appendix A.

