5.2. Efficacy Assessments

Efficacy will be assessed during treatment using the RECIST 1.1 and iRECIST every 9 weeks (every 3 cycles). Intervals can be shortened to 6 weeks (every 2 cycles) if clinically necessary per treating physician. Details on RECIST and iRECIST are described in Appendix B and C. [19, 20] Tumor measurements will be in QIAC.

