7 DATA ANALYSIS AND STATISTICAL CONSIDERATIONS

This is a phase 2, single center, basket study of oral BXCL701 daily on days 1-14 in combination with intravenous PD1/PDL1 antibody on day1 of 21-day cycle in subjects with advanced and refractory malignancies. Lead-in cohort will enroll 6 patients. Only the 6 patients treated at the selected dose during safety lead-in will be assigned to Cohort A or B as appropriate. That is, if there is a dose de-escalation during safety lead-in, then the 6 patients treated at the higher dose will not be assigned to the phase II cohorts. Cohorts A and B will enroll 9 to 17 patients. Response assessments with CT and/or MRI will be done every 9 weeks (3 cycles) following RECIST and iRECIST criteria.[19, 20] Intervals can be shortened to 6 weeks (2 cycles) if clinically necessary per treating physician.

The study will follow the BOP2 design with the following operating characteristics.

Power: 0.80

Type I error: 0.05

P0:0.05**P1:**0.25

Each cohort will enroll 9 patients. If there is no complete (CR) or partial response (PR) in the first 9 patients the enrolment to that cohort will stop. If there ≥ 1 PR or CR in the first 9 patients the enrollment will continue to enroll total of 17 patients. PR or CR does not require confirmation. The treatment will be considered promising for further exploration if ≥ 3 CRs or PRs are observed in 17 patients. The expected **Sample Size** will range from 9 (if terminated after safety lead in) to 34 patients. Accounted for ~20% of patients not being evaluable for efficacy, the actual number of patients to be recruited for the trial will range from 11 to 42.

Scenarios (PA, PB)	Pr(reject H0 for cohort A)	Pr(reject H0 for cohort B)	Average sample size for cohort A	Average sample size for cohort B
(0.05,0.05)	0.046	0.046	12.0	12.0
(0.05,0.25)	0.046	0.813	12.0	16.4
(0.25,0.25)	0.813	0.813	16.4	16.4
(0.05,0.15)	0.046	0.455	12.0	15.1
(0.15,0.15)	0.455	0.455	15.1	15.1
(0.15,0.25)	0.455	0.813	15.1	16.4

Operating characteristics:

Note: PA is the response rate for cohort A, PB is the response rate for cohort B.

The Investigator is responsible for completing toxicity/efficacy summary reports and submitting them to the IND office Medical Affairs and Safety Group for review. These should be submitted as follows:

• Lead-In Stage:

After the first 6 evaluable patients, complete cycle 1 of study treatment. IND Office approval must be obtained prior to advancing to the efficacy stage.

• Efficacy Stage:

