8.5.1 Discontinuation/Withdrawal Criteria

- A patient may be withdrawn by the investigator or the supporting company if he/she violates the study plan or for administrative and/or other safety reasons.
- The patient withdraws consent at any time after agent administration. Every effort will be made to determine why any subject withdraws from the study prematurely.

- The patient is lost to follow-up. A genuine effort must be made to determine the reason(s) why a patient fails to return for the necessary visits. If the subject is unreachable by telephone, a registered letter, at the minimum, should be sent requesting him/her to contact the clinic.
- Disease progression. RECIST 1.1 and iRECIST will be used for assessment of tumor response for the purposes of managing patients on protocol treatment and decision making for discontinuation of study therapy due to disease progression. Response assessments with CT and/or MRI will be done every 9 weeks (3 cycles) following RECIST and iRECIST criteria (intervals can be shortened to 6 weeks if clinically necessary per treating physician). Patients with disease progression per RECIST and/or iRECIST can continue on therapy for clinical benefit if deemed appropriate by the investigator.
- The patient starts a new anti-cancer therapy
- There is a need for any treatment not allowed by the protocol
- Any life-threatening AE.

Any adverse experiences that are present at the time of discontinuation/withdrawal should be followed in accordance with the safety requirements outlined in Section 5.3 Safety Assessments.

Patients who discontinue study treatment who have not shown disease progression and have not withdrawn consent will continue to be followed for disease progression and survival.

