Abbreviations: BP = blood pressure; CxDx = Cycle (number) Day (number); CBC = complete blood count; CT = computed tomography; ECOG = Eastern Cooperative Oncology Group; EOT = End of Treatment; FU = follow-up; HR = heart rate; MRI = magnetic resonance imaging; RR = respiratory rate.

a. After discontinuation of study drugs, patients will complete an EOT visit within 21 days after the last study drug dose.

Protocol 2019-0748 08 Apr 2022

- b. A Safety Follow-up Visit is to be conducted 30 days (±7 days) after the last dose of study drug and later if drug-related AEs have not resolved at that time. Thereafter, patients without documented disease progression (PD) will be followed every 90 days for disease assessments until documentation of PD. After documentation of PD, patients will be followed every 90 days for survival status; such follow-up will likely be conducted by telephone.
- c. Day 1 of Cycle 2 and all subsequent cycles will be 21 days (± 3 days) after the previous dose of study drug was administered.
- d. Tumor assessment must include cross-sectional imaging (MRI or CT scanning with intravenous contrast whenever possible) of the chest/abdomen/pelvis plus whole-body bone scan. Other body sites (e.g., neck) to be included as clinically indicated. Tumor assessment to be performed at Screening, C4D1 (±7 days), C7D1 (±7 days), C10D1 (±7 days), and Day 1 (±7 days) of every 3rd cycle thereafter and at EOT. Intervals for scans can be shortened to 6 weeks (e.g. C3D1, C5D1 etc.) if clinically necessary per treating physician.
- e. Serum chemistry to include: sodium (Na), potassium (K), chloride (Cl), bicarbonate, calcium (Ca), magnesium (Mg), phosphate, blood urea nitrogen (BUN)/creatinine (Cr), and lactate dehydrogenase (LDH).
- f. Liver function tests include aspartate aminotransferase, alanine aminotransferase, alkaline phosphatase, total bilirubin, and albumin.

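### Section 3 stops scheduled tumor scans at PD while Section 5.2 and Appendix A continue them during treatment; if Section 3 is followed, iRECIST responses after a first progression can be missed

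*Combined protocol and SAP*

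**What the plan says.** Section 3 (Study Design Features) sets the first on-treatment tumor assessment at the end of Cycle 3, "and then approximately every 9 weeks thereafter until development of progressive disease (PD"), and adds one at the EOT visit. The same part of Section 3 says that during treatment patients will "have study evaluations performed as detailed in the Schedule of Assessments (Appendix A").

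The other texts on scan timing are:

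- Section 5.2: "Efficacy will be assessed during treatment using the RECIST 1.1 and iRECIST every 9 weeks (every 3 cycles").
- Appendix A footnote d: "Tumor assessment to be performed at Screening, C4D1 (±7 days), C7D1 (±7 days), C10D1 (±7 days"), then every third cycle, and at EOT. It has no stop at PD.
- Section 7: "Response assessments with CT and/or MRI will be done every 9 weeks (3 cycles) following RECIST and iRECIST criteria". No end point is given.
- Section 8.5.1: assessments are "done every 9 weeks (3 cycles) following RECIST and iRECIST criteria (intervals can be shortened to 6 weeks" if clinically necessary). No end point is given.
- Appendix A footnote b, for the period after the 30-day safety visit: "Thereafter, patients without documented disease progression (PD) will be followed every 90 days for disease assessments until documentation of PD".

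Sections 5.7 and 8.5.1 let the investigator keep a patient on therapy after progression by RECIST, iRECIST or both. Section 2.1 makes response rate by RECIST and by iRECIST a primary objective in each cohort. Appendix C allows iCR or iPR after one or more instances of iUPD, but not after iCPD, and requires progression to be confirmed.

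**The concern.** What iRECIST can add to RECIST 1.1 on response is a response that appears after a first, unconfirmed progression. Seeing it requires a scan after that progression. The Section 3 sentence ends scheduled scans at PD, and the documents define PD only in RECIST 1.1 terms (Appendix B), so it ends them at the point where the two criteria start to differ. A patient kept on drug after first PD would then have no scheduled scan until EOT. An iPR that developed and was lost in between would not be recorded, and the iRECIST rate would be pulled down toward the RECIST 1.1 rate. Section 5.2 and footnote d would have scanned the same patient throughout. One primary result could therefore depend on which sentence a team happens to follow.

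**Working it through.** **Inputs.** Cycles last 21 days (Section 6). Scan visits are C4D1, C7D1, C10D1, every third cycle thereafter, and EOT (footnote d). On EOT timing, "patients will complete an EOT visit within 21 days after the last study drug dose" (footnote a). A full cohort has 17 patients (Section 7). Days are nominal, with the ±7-day windows ignored. First PD at C4D1 and continuation through C10D1 are assumptions for illustration.

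**Step 1: reproduce the plan's timing.** Day 1 of cycle k is day 1 + 21(k − 1). So C4D1 = 1 + 63 = day 64, which is 63 days, or 9 weeks, after the first dose. This agrees with the first assessment in Section 3, so the texts share the same first scan and the same interval.

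**Step 2: set the stopping rules side by side.**

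| Text | Frequency | When on-treatment scans end |
|---|---|---|
| Section 3 | 9 weeks | PD, then EOT only |
| Section 5.2 | 9 weeks | covers the treatment period; no stop at PD |
| Footnote d | every third cycle | EOT; no stop at PD |
| Sections 7 and 8.5.1 | 9 weeks | not stated |

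Section 3 conflicts directly with 5.2 and footnote d. Sections 7 and 8.5.1 only lack its stopping rule. Footnote b starts after the 30-day safety visit and concerns patients without PD, so it does not end on-treatment scans.

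**Step 3: identify the patients affected.** Patients who stop drug at first PD have only the EOT scan under either text. The schedules differ only for patients treated past first PD under 5.7 or 8.5.1.

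**Step 4: count scans for such a patient.**

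- First PD at C4D1: day 64.
- C7D1 = 1 + 21 × 6 = day 127, which is 127 − 64 = 63 days after PD.
- C10D1 = 1 + 21 × 9 = day 190, which is 190 − 64 = 126 days after PD.
- Scheduled scans after PD and before EOT: 0 under Section 3, 2 under footnote d.
- If the day 190 dose is the last, EOT is due by day 190 + 21 = 211. Under Section 3 the next scheduled scan could then fall up to 211 − 64 = 147 days after the PD scan.

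**Step 5: see what can be lost.** Under RECIST 1.1 no response can follow progression (Appendix C comparison table), so that rate is the same under either schedule. Under iRECIST, an iCR or iPR gained after day 64 and lost before EOT is missed under Section 3. One still present at EOT is caught.

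**Step 6: size per event.** One unrecorded responder in a 17-patient cohort lowers the iRECIST rate by 1/17 = 0.0588, or 5.9 percentage points. This is a unit, not an estimate of the loss.

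**Step 7: check the design figures.** The probability of declaring the treatment promising is the sum over x = 1 to 9 of P(X1 = x) × P(X2 ≥ 3 − x), with n1 = 9 and n2 = 8. It gives 0.0466, 0.4559 and 0.8122 at true rates 0.05, 0.15 and 0.25, against 0.046, 0.455 and 0.813 in Section 7. Average sample sizes are 11.96, 15.15 and 16.40, against 12.0, 15.1 and 16.4. The design is reproduced closely, and none of these figures uses the scan schedule.

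**The case against.** The best defense is that the operative schedule is already right. Section 3 itself sends on-treatment evaluations to Appendix A, and footnote d lists scans visit by visit through EOT. A site working from Appendix A loses nothing. By default, drug also stops at progression (Sections 6.1 and 6.5), so scanning until PD and scanning during treatment nearly coincide. A lost response needs a chain of events: first PD, a discretionary decision to continue, a later iPR, loss of that iPR before EOT, no unscheduled scan in between, and a team that follows the Section 3 sentence over Appendix A. The protocol permits treatment past progression but does not say how often it will happen.

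All of this stands as a limit on size. It does not remove the conflict. Section 3 gives a specific stopping rule alongside its pointer to Appendix A, and nothing says which prevails. Reading PD as iCPD would remove the loss, since Appendix C allows no response after iCPD, but the documents do not define PD that way.

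Two stronger readings should be set aside. A reader might infer that Section 3 contradicts four other places; Sections 7 and 8.5.1 are only silent on stopping. A reader might also infer that patients who stop drug at first PD are affected; both schedules give them the same EOT scan.

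**Conclusion.** The inconsistency is real and bears on how one primary endpoint is ascertained. If the Section 3 sentence is followed, a patient treated past first PD has no scheduled scan until EOT, and an iRECIST response gained and lost in that time is missed. Any resulting bias in the iRECIST rate is downward. In the worked case the difference is 0 scans against 2, and each missed responder costs 5.9 points in a cohort of 17. This rests on the RECIST 1.1 definition of PD, nominal visit days, and patients actually being continued past progression. Where Appendix A is followed, the loss does not arise.

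A reader might go further and infer a loss of power. If 5% to 30% of true responders were missed at a true rate of 0.25, the chance of declaring the treatment promising would fall from 0.812 to between 0.781 and 0.566. Those shares are pure assumptions with no support in the documents. Section 7 also does not say that its CR and PR counts are iRECIST responses. The number of lost responses cannot be derived, the RECIST 1.1 rate is unaffected, and no change to the 1/9 or 3/17 boundaries is claimed.

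**What to change.** In Section 3, replace the words that end scheduled scans at PD with: *for as long as the patient remains on study treatment, including after a first RECIST PD (iUPD), per Appendix A footnote d; after treatment ends, footnote b applies.*

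The end point should be study treatment, not iCPD. Sections 5.7 and 8.5.1 also allow therapy after progression by iRECIST, so stopping scans at iCPD would leave a mismatch with footnote d for those patients. The pointer to footnote b keeps the 90-day assessments for patients who stop drug without progression.

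The cost is one phrase in a protocol amendment. It needs no scan beyond those already in footnote d, no added patients, and no change to the Section 7 decision rules.

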3.1 Justification for Dose

In a previously conducted multiple dose clinical study by Point Therapeutics with single agent BXCL701 (CA168-002), there was a dose dependent increase in plasma IL-6 in subjects receiving daily doses of BXCL701 from 0.3 to 1.2 mg when measured on Day 7. At doses ≥ 0.1 mg, pronounced inhibition of plasma CD26/DPP-IV activity to $\leq 20\%$ of baseline was apparent within 1 hour of dosing, and at doses of ≥ 0.3 mg, CD26/DPP-IV activity was almost completely inhibited (>95%) within 30 minutes of the first dose on Day 1. These pharmacologic data suggest that daily doses of 0.4 to 0.6 mg BXCL701 provide maximum pharmacodynamic inhibition, as measured by inhibition of plasma CD26/DPP-IV while also providing significant cytokine (IL-6 and G-CSF) upregulation over baseline.

BioXcel has considered the clinical AE profile of each therapeutic, BXCL701 and pembrolizumab, to clinically combine them. Based upon results from completed clinical trials, single agent BXCL701 is associated with AEs that are generally mild, manageable, and reversible. The most frequently observed AEs that appear to be characteristic of BXCL701 are edema/peripheral swelling, hypotension, dizziness, and hypovolemia. These events, including edema, tend to be manageable and reversible and usually resolve following a drug hold. The most common AEs associated with pembrolizumab include anemia, fatigue, hyperglycemia, hyponatremia, itching, cough, and nausea. A comparison of the safety profiles of BXCL701 and pembrolizumab does not indicate clinically significant overlapping potential toxicities. Given the lack of overlapping toxicities when the 2 agents are combined, it is expected that there will be no more toxicity than the sum of the individual toxicities observed at the maximum tolerated dose of each agent. Nonetheless, the starting dose for BXCL701 in combination with pembrolizumab is

proposed to be 0.6 mg daily, i.e., the previously identified recommended Phase 2 dose. The dose will be divided into two doses (0.3 mg twice a day) to minimize the risk of hypotension. Based on a review of emerging data from the BXCL701 program, the dosing schedule in the Efficacy Stage will be modified to implement a step-up dosing schedule during Cycle 1. The intent of step-up dosing is to immediately address a potentially serious side effect of hypotension that appears most likely to occur during the first week of treatment in Cycle 1. BioXcel has evaluated BXCL701 0.4 mg total daily dose with pembrolizumab during Phase 1b of the prostate cancer study and it was well-tolerated, with no DLTs experienced. In the Phase 1b cohort, none of the three patients experienced adverse events consistent with cytokine activation considered related to BXCL701. Therefore, the Bioxcel program is incorporating a one-week lead-in dosing period of 0.2 mg BID to potentially mitigate the effects of cytokine activation, including hypotensive events, which seem to predominantly occur during the first week of treatment in patients starting with 0.3mg BID. Escalation to 0.3 mg BID in patients demonstrating tolerance after one week of treatment is important since it is the dose that was previously associated with objective responses during prior development of BXCL701. Therefore, starting from Protocol version 7, new patients enrolled will be administered BXCL701 at the starting dose of 0.2 mg orally twice a day for the first 7 days. If well tolerated and in the absence of signs and symptoms of clinically significant hypotension the dose will be escalated to 0.3 mg orally twice a day.

4 STUDY POPULATION

Approximately 6 to 12 and 24 to 48 patients who fulfill the eligibility criteria of the protocol will be enrolled during Lead-in and Efficacy Stages of the protocol, respectively. Patients enrolled to the Lead-in Stage will be evaluated and used for the efficacy stage.

4.1. Eligibility Criteria

All patients must satisfy the following inclusion and exclusion criteria to be eligible for entry into the trial.

4.1.1 Inclusion Criteria

- 1. Patient with a histology or cytology proven solid advanced cancer, which failed or is intolerant of standard therapies known to offer survival benefit unless standard therapies include PD1 or PD-L1 antibodies.
 - a. Lead-in stage: patient with advanced cancers meeting the criteria above with or without prior treatment with PD1/PDL1 and/or CTLA-4 targeted therapies. Patients with prior treatment with PD1/PDL1 targeted therapies should be relapsed.
 - b. Efficacy stage cohort A: patients with advanced cancers not previously treated with PD1/PDL1 and/or CTLA-4 targeted therapies.
 - c. Efficacy stage cohort B: patients with advanced cancers which have relapsed or progressed with PD1/PDL1 and/or CTLA-4 targeted therapies
- 2. Patient with a life expectancy of more than 3 months, in the opinion of the investigator.
- 3. Patient has Eastern Cooperative Oncology Group (ECOG) performance status of 0-2.

- 4. Patient is ≥ 12 years of age. Patients < 18 years of age have to weigh ≥ 40 kgs.
- 5. Patients must have measurable disease by RECIST 1.1 and iRECIST. Disease amenable to a biopsy is not mandatory. However, pre and post treatment biopsies (see Appendix A) are mandatory if deemed medically safe and feasible for arms, which advanced to Stage 2 of Efficacy Stage (BOP2).
- 6. Patient's acute toxic effects of previous anticancer therapy have resolved to \leq Grade 1 except for Grade 2 peripheral neuropathy or any grade of alopecia.
- 7. Patient has adequate baseline organ function, as demonstrated by the following:
 - a. Serum creatinine ≤ 1.5 times institutional upper limit of normal (ULN) or calculated creatinine clearance >40 mL/min;
 - b. Serum albumin ≥ 2.5 g/dL;
 - c. Total bilirubin $\leq 1.5 \times$ ULN (for patients with known Gilbert syndrome $\leq 3 \times$ ULN);
 - d. Aspartate aminotransferase (AST) and alanine aminotransferase (ALT) \leq 3 × institutional ULN (patients with hepatic metastases must have AST/ALT \leq 5 × ULN).
- 8. Patient has adequate baseline hematologic function, as demonstrated by the following:
 - a. Absolute neutrophil count (ANC) $\geq 1.0 \times 10^{9}$ /L.
 - b. Hemoglobin ≥ 8 g/dL and no red blood cell transfusions during the prior 7 days.
 - c. Platelet count $\geq 75 \times 10^9$ /L.
- 9. Women of childbearing potential must have a negative serum or urine pregnancy test (minimum sensitivity 25 IU/L or equivalent units of human chorionic gonadotropin [HCG]) within 14 days prior to the initiation of treatment and/or postmenopausal women must be amenorrheic for at least 12 months to be considered of non childbearing potential. Women of childbearing potential must agree and commit to the use of 2 highly effective methods of birth control throughout the duration of the study until at least 4 months following the last dose of study drug. Acceptable methods are defined as those that result, alone or in combination, in a low failure rate (ie, less than 1% per year) when used consistently and correctly, such as surgical sterilization, an intrauterine device, or hormonal contraception in combination with a barrier method. It is currently unknown whether BXCL701 or pembrolizumab may reduce the effectiveness of systemically acting hormonal contraceptives; therefore, women using systemically acting hormonal contraceptives should add a barrier method. In certain countries (if permitted by law), WOCBP may agree to abide by heterosexual abstinence during the time of participation in this study.
- 10. Male patients and their female partners of childbearing potential must agree and commit to use a barrier contraception (eg, condom with spermicidal foam/gel/film/cream/suppository) throughout the duration of the study until at least 60 days following the last dose of study drug, in addition to their female partners using either an intrauterine device or hormonal contraception and continuing until at least 4 months following the last dose of study drug. This criterion may be waived for male patients who have had a vasectomy > 6 months before signing the ICF.
- 11. Patient has signed informed consent prior to initiation of any study-specific procedures or treatment.

12. Patient is able to adhere to the study visit schedule and other protocol requirements.

